### 6.1.2. Definition of Study Baseline

Unless otherwise specified, for efficacy and health outcomes, baseline is defined as the last nonmissing assessment recorded on or prior to, the first date that clinical status is assessed.

Baseline for safety analyses is described in [Table KHAA.6.8](#).

Change from baseline will be calculated as the visit value of interest minus the baseline value. If a baseline value or the value at the visit is missing for a variable, then the change from baseline is defined as missing.

The baseline of vital signs is defined as the vital signs collated at Day 1 from the case report form (CRF) Assessment for the National Early Warning Score (NEWS) (AVPU1001\_VS1001\_F1). The post baseline vital signs for analyses other than NEWS is defined as vital signs collated from CRF Vital Signs: Minimum and Maximum (VS1001).

### 6.1.3. Study Time Intervals

To calculate the length of any time interval or time period in this study, the following formula will be used:

$$\text{Length of interval (days)} = \text{End Date} - \text{Interval Start Date} + 1$$

To convert any time length from days to weeks, the following formula will be used:

$$\text{Length of interval (weeks)} = \text{Length of interval (days)} / 7$$

Only for the purpose of calculating the length of study period time intervals, the words “prior to” in [Table KHAA.6.2](#) should be understood to mean “the day before” while the words “after” should be understood to mean “the day after.” For the purpose of determining whether a date/time lies within an interval, these words are intended to convey whether the start or end of the period is inclusive of the specified date.

**Table KHAA.6.2. Definition of Study Period Time Intervals**

Study Period	Interval Start Definition	Interval End Definition
Screening: All participants who sign informed consent are considered as entering the Screening Period.	Informed consent date	Prior to the start of Treatment Period.
Post-Treatment Follow-Up: All participants who had a follow up visit are considered as entering follow-up period.	After the Treatment Period ends.	The maximum of the last study visit date or study disposition date.

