The Summary of Product Characteristics indicates as special warning and precautions for infections, including tuberculosis (TB), hematological abnormalities, viral reactivation, use of live vaccines, increase in blood lipid parameters, increase in hepatic transaminase, malignancy, VTE, hypersensitivity, and use of baricitinib with potent immunosuppressive medications.

Baricitinib has an established safety profile with a positive benefit/risk profile in RA. An integrated analysis of patients with active RA exposed to baricitinib with 3770 patients and 10,127 patient-years for a maximum exposure of 7 years (as of February 2018) was recently published (Genovese et al. 2019). No significant differences were seen for baricitinib 4-mg versus placebo in adverse events leading to permanent drug discontinuation, death, malignancy,

serious infection, or major adverse cardiovascular events. Malignancy (excluding non-melanoma skin cancer) incidence rates (IRs) per 100 patient-years were 0.8 (2-mg) and 1.0 (4-mg; as-randomized analysis). Fewer than 1% of patients discontinued due to abnormal laboratory results.

Specifically regarding VTE, during the 16-week placebo-controlled period of RA studies, the IRs per 100 patient-years for deep vein thrombosis (DVT)/pulmonary embolism (PE) were numerically higher in baricitinib 4-mg (IR=1.7) versus both baricitinib 2-mg and placebo (IR=0). With long-term exposures, the exposure-adjusted IR of VTE for baricitinib-treated patients with RA was similar to the background rates published in the literature for the target population. Cases observed with baricitinib were confounded by 1 or more recognized risk factors for VTE and the time to onset of an event ranged from 37 to 1658 days.

VTE has been classified as an important potential risk for baricitinib and is also an adverse drug reaction. Mitigation of the risk of venous thromboembolism will be managed through the appropriate exclusion and discontinuation criteria which limit participation of patients who are at an increased risk of VTE (Section 5.2, Section 7.1.1). The addition of VTE prophylaxis to all patients enrolled in this study unless there is a contraindication will also reduce the potential risk (Section 6.5.2).

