## Post-Treatment Follow-up

Safety analyses for the post-treatment follow-up period will be conducted on the follow-up population. Follow-up emergent adverse events, SAEs including deaths, and adverse events that lead to study discontinuation will be summarized. All adverse events, including pre-existing conditions, will be listed by participant, visit, preferred term, treatment group, severity, and relationship to the treatment.

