### 6.1.1. Analysis Populations

The following populations are defined for this study:

Population	Description
Entered	All participants who sign the informed consent form
Intent-to-Treat (ITT)	All participants randomly assigned to study intervention. Participants will be analyzed according to the intervention to which they were assigned.
Per Protocol Set (PPS)	The PPS will include those participants in the ITT population who do not have any identified important protocol violations considered to impact efficacy analyses. Qualifications for, and identification of, significant or important protocol violations will be determined while the study remains blinded, prior to database lock.
Safety	All participants randomly assigned to study intervention and who receive at least 1 dose of study intervention and who did not discontinue from the study for the reason 'Lost to Follow-up' at the first postbaseline visit. Participants will be analyzed according to the intervention they actually received.
Follow-up	All randomized participants who received at least 1 dose of investigational product and have entered the post-treatment follow-up period. Participants will be analyzed according to the intervention to which they received.

A listing of patients who were randomized but did not receive study drug will be prepared. This listing will include baseline information and their last known status.

A sensitivity analysis for the primary efficacy analysis will exclude patients who die within 24 hours of randomization and have Do Not Resuscitate (DNR) or Do Not Intubate (DNI) in ITT analysis populations will be conducted.

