#### **6.13. Safety Analyses**

The planned safety analyses are consistent with compound level safety standards, which are based on various sources, including company standards, internal and external subject matter experts, and cross-industry initiatives (for example, white papers produced by a Pharmaceutical Users Software Exchange [PhUSE] Computational Science Working Group [a collaboration with Food and Drug Administration (FDA) and PhUSE], published in the PhUSE Deliverables Catalog [PhUSE [WWW]]. Descriptions of the safety analyses are provided in this SAP; however, some details are in compound level safety standards.

A treatment-emergent adverse event (TEAE) during the analysis period is defined as an event that either first occurred or worsened in severity after the first dose of study treatment and on or prior to the end of the postbaseline period (defined as Day 28 for the primary outcome datalock).

A follow-up-emergent adverse event (FEAE) is defined as an event that either first occurred or worsened in severity after the treatment period and on or prior to the last visit date during the post-treatment follow-up period (up to the Day 60 visit) of the study.

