**Table KHAA.6.9. Summary Tables Related to Adverse Events**

Analysis	Population or Analysis Set
An overview table, with the number and percentage of subjects who experienced a TEAE, serious adverse event, death, discontinued from study treatment due to an adverse event	Safety population
An overview table, with the number and percentage of subjects who experienced an event, serious adverse event, death, discontinued from study due to an adverse event	Follow-up analysis set
The number and percentage of subjects with TEAEs using MedDRA Preferred Term nested within System Organ Class	
The number and percentage of subjects with FEAEs using MedDRA Preferred Term nested within System Organ Class	Follow-up analysis set
The number and percentage of subjects with TEAEs using MedDRA Preferred Term	Safety population
The number and percentage of subjects with TEAEs by maximum severity using MedDRA Preferred Term	Safety population
The number and percentage of subjects with TEAEs using MedDRA Preferred Term for the common TEAEs (occurred in $\geq 2\%$ before rounding of treated subjects)	Safety population
The number and percentage of subjects who experienced a serious adverse event (including deaths and SAEs temporally associated or preceding deaths) using MedDRA Preferred Term nested within System Organ Class	Safety population
The number and percentage of subjects who experienced a serious adverse event (including deaths and SAEs temporally associated or preceding deaths) using MedDRA Preferred Term nested within System Organ Class	Follow-up analysis set
Listing of All SAEs	Safety population
The number and percentage of subjects who permanently discontinued from study treatment due to an adverse event (including adverse events that led to death) using MedDRA Preferred Term nested within System Organ Class	Safety population
Listing of AEs which led to permanent discontinuation from the study treatment and from the study	Safety population

Abbreviations: AEs = adverse events; ITT = Intent-to-Treat; MedDRA = Medical Dictionary for Regulatory Activities; SAE = serious adverse event; TEAE = treatment-emergent adverse event.

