#### 1.1) Additional analyses for the main study (Day 60)

The following table gives planned analyses for the main study using Day 60 data.

Variable	Population	Analysis Method	Time Point	Groups/Subgroups
Observed OS values at Day 60	ITT population with a baseline NIAID OS and a value at the Day 60 Visit	Descriptive statistics as described in Table KHAA.6.1 for categorical/discrete data.	At the Day 60 visit.	Overall and by baseline 
 
• OS 4, 5, 6 and 5, 6 combined.
 
• Corticosteroid status (see Section 6.1.4)
 
• Age group (<65, ≥65)
 

All-cause mortality:	Patients in the ITT population, excluding randomized patients who discontinued on the day of randomization and have no baseline or postbaseline OS data.	Time to death from all causes, all time on study. Event dates are date of death for patients who died. Censor dates are last known information that indicates patient was alive. Patients who die after the visit window for Day 60, will be censored at the last date of their Day 60 visit window. KM curves and standard summary statistics (see Section 6.2.3 ) will be generated.	From baseline to end of study participation.	

Additionally, the following analyses will be performed after the Day 60 database lock for relevant subsets of the ITT population.

- Demographics
- Disposition
- Concomitant medications
- Safety analyses will include all adverse events occurring post primary outcome datalock up to an including Day 60. The following are the planned safety analyses:
  - Follow-up-emergent adverse events (FEAEs). FEAE is defined as an event that either first occurred or worsened in severity after Day 28 and on or prior to end of the study.
  - Serious adverse events
  - Adverse events leading to death
  - Overview of infections (includes herpes zoster, herpes simplex, opportunistic infections, and tuberculosis)

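### As written, the Follow-up set can exclude patients who die or are lost after Day 28 but before any follow-up visit, and Appendix 3 gives two conflicting starts for its Day 60 safety window

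*SAP*

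**What the plan says.** **Who is in the set.** SAP 6.1.1 defines the Follow-up population as "All randomized participants who received at least 1 dose of investigational product and have entered the post-treatment follow-up period". What entering means is stated only in Table KHAA.6.2: "All participants who had a follow up visit are considered as entering follow-up period". The interval begins "After the Treatment Period ends". The table has no row for the treatment period itself, but SAP 5.1 runs its evaluations to Day 28.

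**What the set is used for.** Protocol 9.4.4 says "Safety analyses for the post-treatment follow-up period will be conducted on the follow-up population". SAP Table KHAA.6.9 assigns three tables to it: an overview of patients who "experienced an event, serious adverse event, death, discontinued from study due to an adverse event", follow-up-emergent adverse events (FEAEs) by preferred term, and SAEs, including deaths, by preferred term.

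**Where the other tables stop.** SAP 6.13 counts a treatment-emergent event only if it occurs "on or prior to the end of the postbaseline period (defined as Day 28 for the primary outcome datalock".

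**When follow-up visits occur.** Protocol 1.3 and 4.1 place the first about 28 days after last dose, with a tolerance of 4 days either way, and the second at about Day 60. Both may be by telephone.

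**Appendix 3, section 1.1.** The Day 60 safety lead-in reads "Safety analyses will include all adverse events occurring post primary outcome datalock up to an including Day 60". The first item under it, FEAEs, instead starts after Day 28. The items for SAEs, adverse events leading to death, and infections give no start of their own. These analyses run on unspecified subsets of ITT, not on the Follow-up set.

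**The concern.** A table of deaths and SAEs should not require the patient to have survived, or stayed in contact, until a visit. Under the literal entry rule it does. A patient who dies early in the follow-up period is removed from the count of deaths and from the group at risk. Membership is also decided after randomisation, so the two arms' Follow-up sets need not be comparable. The gap is longest for patients dosed through Day 14, that is, those still in hospital then and slowest to recover.

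The Appendix 3 wording raises a different question on different tables. If the SAE, fatal-event and infection items take their start from the lead-in, and the datalock is one calendar date, most patients will have passed Day 60 before the window opens.

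**Working it through.** The plan states no figure on this point, so there is none to reproduce. The check traces one patient through the definitions and then does the day arithmetic.

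**1. A traced case.** A patient is dosed to Day 14, has a serious event on Day 33 and dies on Day 35 before any follow-up contact.
- Treatment-emergent tables: not counted, because Day 33 is after Day 28.
- Table KHAA.6.9 follow-up tables: not counted in numerator or denominator, because there was no follow-up visit.
- ITT Day 60 all-cause mortality (Appendix 3): the death is counted; no visit is required.
- Listing of all SAEs on the Safety population (Table KHAA.6.9): a reported SAE is listed.
- Registry summary (SAP 6.19): a reported SAE is counted by arm, since seriousness there does not depend on being treatment-emergent.
- Appendix 3 FEAEs: not excluded by the window. Appendix 3 SAEs and fatal events: depends on what datalock means.

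**2. Length of the gap.** First visit = last dose day + 28, with a tolerance of ±4. Gap = days from Day 29 to the day before the visit = visit day − 29, with a floor of 0.

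| Last dose | Visit, nominal (window) | Gap, nominal | Gap across window |
|---|---|---|---|
| Day 14 | Day 42 (38-46) | 13 days (Days 29-41) | 9-17 days |
| Day 7 | Day 35 (31-39) | 6 days | 2-10 days |
| Day 1 | Day 29 (25-33) | 0 days | 0-4 days |

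Days 29 to 60 span 32 days, so for a last dose on Day 14 the nominal gap is 13/32 = 41% of the period.

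**3. The Appendix 3 window.** Protocol 9.5 places the primary lock after all participants have completed or discontinued the treatment period, which is a single calendar event. SAP 6.13 and Table KHAA.6.8 instead link the primary outcome datalock to a Day 28 cut. Each reading has support in the documents.

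- *Day 28 cut:* all 32 days are covered for every patient, so 100%.
- *Calendar date:* assume uniform accrual over D days and a lock L days after the last patient's Day 28. A patient randomised s days before the last one has 32 − s − L days left. Share of patients with any time left = (32 − L)/D. Share of Day 29-60 person-time covered = (32 − L)²/(64·D).

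| D (assumed) | L (assumed) | Patients with any time left | Person-time covered |
|---|---|---|---|
| 120 | 0 | 32/120 = 26.7% | 1024/7680 = 13.3% |
| 270 | 0 | 32/270 = 11.9% | 1024/17280 = 5.9% |
| 120 | 14 | 18/120 = 15.0% | 324/7680 = 4.2% |
| 270 | 14 | 18/270 = 6.7% | 324/17280 = 1.9% |

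The documents give neither accrual length nor lock lag, so these are ranges under assumption.

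**The case against.** **The rule says all, not only.** Table KHAA.6.2 does not say that a patient without a visit stays out. That is true, but no other entry rule is given, so a programmer would apply this one. Either follow-up visit qualifies and telephone is allowed, so missing the first visit alone excludes nobody. That confines the problem to patients who die or are lost before any follow-up visit; it does not remove it.

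**The events are visible elsewhere.** A reader might infer that deaths and SAEs after Day 28 disappear from the trial's reporting. The documents do not support that: the mortality analysis, the SAE listing and the registry summary all retain them. What stands is that the tables built for this period can be incomplete. A listing is not a comparison by arm, and the mortality analysis does not cover non-fatal SAEs.

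**Appendix 3 already says after Day 28.** A reader might infer that the Day 60 safety analyses start at the lock date. That is not settled, because the FEAE item contradicts it and the main SAP text ties the datalock to Day 28. This is a contradiction to reconcile, and it affects only the items with no window of their own. Nor does the visit condition carry into Appendix 3. Equally, its ITT subsets are not specified, so it cannot be relied on to repair the Follow-up tables.

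**Venous thromboembolism.** A reader might add that Appendix 3 has an infection overview but none for VTE, and cite the protocol's statement that "the time to onset of an event ranged from 37 to 1658 days". That figure describes rheumatoid arthritis patients in a passage on long-term exposure, not a course of at most 14 days. VTE is already a special safety topic in SAP 6.13.5, and FEAEs are tabulated by preferred term. A separate overview would be a preference; its absence is not an error.

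**Conclusion.** The point holds as a wording defect with a real consequence for a limited set of tables. Taken literally, the Follow-up set selects on the outcome it reports. The exposed interval is Days 29-41 nominally for a last dose on Day 14 (9-17 days across the visit window), 2-10 days for a last dose on Day 7, and 0-4 days for Day 1. This rests on the visit rule being the only operative entry rule.

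The number of deaths or SAEs affected cannot be given, because the documents contain no event rate for that interval. Protocol 8.3.1 also keeps events caused by COVID-19 progression off the SAE form unless they are judged possibly related to treatment, so deaths in the gap should not be equated with missing SAEs. Differing losses between arms are possible, but nothing in the documents shows them.

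The Appendix 3 conflict is separate and less certain. Coverage of Days 29-60 for the SAE, fatal-event and infection items is 100% under one reading and about 6-13% under the other (accrual of 120-270 days, no lock lag, both assumed).

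**What to change.** - In SAP 6.1.1, define the Follow-up set as all dosed patients in the Safety population not known to have died on or before Day 28, whether or not a follow-up visit took place. This keeps patients who withdrew early but have later follow-up information; a condition of still being in the study at Day 28 would drop them.
- Remove the visit condition from Table KHAA.6.2.
- In Appendix 3, section 1.1, replace the datalock wording and state that every safety item counts events with onset or worsening after the patient's own Day 28.

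The cost is SAP wording and reprogramming of the set flag; no new data are needed. The small downside is that some members of the set will have no visit data and will contribute only reported events.

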### 6.1.4. Baseline Stratification Variables

Throughout the SAP, when baseline stratification variables are referred to, they include the following categorical variables:

- baseline disease severity (ordinal scale [OS] 4, OS 5, OS 6),
- age (<65 years, ≥65 years),
- region (US, Europe, rest of world) and
- dexamethasone and/or other systemic corticosteroid used at baseline for primary study condition (Yes/No).

If any of these are redundant for a particular model they will be dropped.

